### 4.2 SCIENTIFIC RATIONALE FOR STUDY DESIGN

The age range (13-17) was chosen because it captures a key developmental stage, during which glycemic control often deteriorates. Adolescents who have been diagnosed with diabetes for at least 12 months will be studied to avoid confounding the effects of the initial adjustment period after diagnosis. A validated scale of diabetes distress in adolescents, the Problem Areas in Diabetes-Teens scale (PAID-T), will be used to screen adolescents for DD. A parent/Legally Authorized Representative will be eligible if he/she is currently living with the adolescent.

### 4.3 JUSTIFICATION FOR INTERVENTION

#### Education Only Intervention (EDU):

The control condition (EDU) was selected based on positive affect studies in adults with chronic health conditions. Adolescents randomized to the EDU intervention will complete a health behavior contract, which has been shown to improve diabetes management in other studies of adolescents with T1D. The health behavior contract states the behavior that they are committing to do (e.g., check blood glucose 4 times/day), when they will do it (e.g., before meals and before bedtime), and how often they will perform the target behavior (e.g., daily). They will also receive an education packet (14 pages) based on content from the American Diabetes Association website: [www.diabetes.org](http://www.diabetes.org) with appealing graphics and simple language. Additionally, adolescents will receive a retention item halfway through the 8-week intervention period.

#### PA + Education Texting Intervention (TXT):

In addition to completing the health behavior contract, adolescents randomized to the PA + Education intervention condition will complete the Positive Affect Interview developed in our pilot work. During the first study visit, a trained RA will guide the adolescents through the following empirically-validated

exercises to induce positive affect, and their answers will be included in the tailored text messages (see Table 1 for a description of PA components):

1. Gratitude: Adolescents will be told that research shows that feeling happy helps people to handle challenges in their lives. We will ask them, “what are some small things that make you feel good, even for a few minutes (e.g., hearing your favorite song?”). Based on their answers, they will receive tailored text messages (updated weekly with new responses). “Last week you said [MUSIC] made you happy. Have you noticed that this week, even for a few minutes? (Please reply) Is there something else that has made you feel happy this week? Please reply yes or no (if yes: What is it?) That’s great!”

2. Self-Affirmation: Adolescents will choose from a list of Important Values, based on self-affirmation studies conducted with adolescents: Enjoying Sports, Art, Working Hard in School, Having a Sense of Humor, Being Creative, Belonging to a Social Group or Club, Following Politics or Current Events, Relationships with Friends, Relationships with Family, Faith or Spirituality, Music. The important value selected by adolescents will be piped into their tailored text messages. “You mentioned that [ART] was important to you. And I asked you to think about that when it was hard for you to take care of diabetes. Have you done that this week? (Please reply). Remember, focus on [ART] when it is time to take care of diabetes!

3. Mood Boosters: Adolescents will also receive brief messages intended to boost their mood, similar to those used in other studies. In our pilot work, we asked teens to rate potential mood booster messages, consisting of inspirational quotes (e.g., “Keep your eyes on the stars and your feet on the ground - Theodore Roosevelt”) or jokes (e.g., “Q: What’s the difference between a fish and a guitar? A: You can’t tuna fish”). Based on their responses, we created Mood Booster message banks for younger teens (ages 13-14) and older teens (ages 15-17) consisting of the highest-rated messages.

4. Unexpected Gifts: Adolescents will be sent an e-gift card code (worth \$5.00) biweekly as another way to increase positive affect. Gifts that are viewed as useful and “delightful” are most effective at inducing positive affect; they do not have to be valuable. In exit interviews conducted during the pilot studies, adolescents reported using Amazon gift cards to download music, videos, and purchase small items, such as socks.

5. Parental Affirmation: We will ask parents to provide praise or positive messages to their adolescents, focused on non-diabetes strengths (e.g., “I heard you practicing your guitar – sounded great!” or “I had a great time when we \_\_\_\_.”) Based on feedback from our pilot studies, we developed a protocol to instruct parents on the types of messages to send, including feedback on a sample message, to ensure that messages are consistent with the study goals. Parents will receive weekly text reminders at preferred times. By asking parents to provide affirmations rather than reminders for diabetes management, we hope to minimize parent-child conflict around diabetes care.

## 5 STUDY POPULATION

### 5.1 INCLUSION CRITERIA

In order to be eligible to participate in this study, an individual must meet all of the following criteria:

- Age 13-17
- Diagnosed with type 1 diabetes for at least 12 months
- Speak and read English
- Report at least moderate diabetes distress on the Problem Areas in Diabetes Scale - Teen version

### 5.2 EXCLUSION CRITERIA

An individual who meets any of the following criteria will be excluded from participation in this study:

1. Currently participating in another intervention
2. Other serious health conditions that interfere with diabetes management

### 5.3 STRATEGIES FOR RECRUITMENT AND RETENTION

Enrollment. We will recruit a sample of 200 adolescents with T1D and their parents from two clinical sites (Vanderbilt University Medical Center and Children's National Medical Center), 100 from each site. The sampling goal for this study across the two sites is 68% white, 10% Hispanic, 16% Black, and 6% Asian, with equal numbers of boys and girls, in line with recent studies conducted in these settings. We will employ a method of enrolling subjects that has been evaluated and refined as part of our prior work.

At CNMC, there are currently **614 active patients** with T1D between the ages of 13-17 years, and there are no current competing studies within this age group. The adolescent patient population is 47% female and 52% Caucasian. Thus, CNMC is well-positioned to provide an adequate and diverse sampling of participants for the proposed study.

At VUMC, there are currently **1100 active patients** between the ages of 13-17, and the adolescent patient population is 48% female and 75% Caucasian. Thus, we do not anticipate difficulty in meeting our enrollment goals.

We created recruitment videos to explain the study in a brief and engaging format:

<https://youtu.be/IQT4REruoQ> (VUMC); [https://youtu.be/Uinw\\_a8\\_5Lo](https://youtu.be/Uinw_a8_5Lo) (CNH)

We will also use Research Match and the Vanderbilt Research Notifications Distribution list to reach more potential VUMC participants.

After completing visit 2 (3 month follow up data collection and exit interview) we will invite 20 youth participants who currently use/have used a CGM to participate in an optional interview to describe the role of CGM on their diabetes management.

Screening. We will screen adolescents for diabetes distress using a validated measure, the Problem Areas in Diabetes-Teens scale (PAID-T). In order to meet our enrollment goals, enrolling 4-5 per month per site, we will plan to screen 10-12 families per week.

Retention & Follow-Up: Efforts will be made to maximize retention across trial assessments. These include providing study retention items (e.g., keychain flashlights, laptop decals with the study logo), sending birthday cards to trial participants, and verifying contact information, including email addresses and phone numbers, at each assessment point. As in previous studies, we will attempt to collect follow-up data in person during regularly scheduled clinic appointments. Prior to their scheduled appointment, families will be reminded of the visit and asked to come early or stay after their appointment. If families cancel or do not show for their appointments, we will email and text a unique link to the REDCap survey and continue to follow up by phone and email until surveys are completed. We will give the family the option of doing a Coremedica HemaSpot-SE HbA1c kit at home if they are unable to come into the clinic to get a point of care A1c test. If families are not responsive, we will send a paper packet with a self-addressed, stamped envelope. These methods have resulted in excellent retention rates (91-98%) in our pilot studies. We will actively work towards maintaining families' participation in data collection regardless of their engagement in the text messages so that intent-to-treat analyses may be conducted. We are conservatively planning for a ~15% attrition rate based on data from our pilot studies to protect against overestimation.

Incentives. In order to promote the completion of trial measures at all assessment points, participants will be compensated for their time at each data collection, with increasing compensation (\$20, \$25, \$30, \$30) to improve retention. In addition, participants will receive \$10 for participating in a qualitative exit interview at the 3-month data collection. Participants who complete the secondary study (interview describing their CGM use) will receive an additional \$30 gift card.

## 6 STUDY INTERVENTION(S) OR EXPERIMENTAL MANIPULATION(S)

### 6.1 STUDY INTERVENTION(S) OR EXPERIMENTAL MANIPULATION(S) ADMINISTRATION

Eligible families will be asked to stay after their appointment to complete enrollment, or they may choose to come back for a study visit. Trained study staff will describe the study in detail to interested families. They will be encouraged to ask questions before giving consent. After obtaining informed consent/assent, adolescents and parents will complete a battery of self-report measures (see below) and will be randomized to the Positive Affect plus Education texting condition (TXT) or the Education only condition (EDU). Adolescents and parents will complete measures again 3 months, 6 months, and 12 months during regularly scheduled clinic visits.

Adolescents and their parents will complete measures on a tablet using REDCap, an electronic database. The survey completion is expected to take 30 minutes.

After completing baseline data, adolescents will be randomized to either the Education group or the text-messaging Positive Affect + Education group (TXT).

#### 6.1.1 Study Intervention or Experimental Manipulation Description

Participants randomized to the EDU group will complete a behavioral health contract. The health behavior contract states the behavior that they are committing to do (e.g., check blood glucose 4 times/day), when they will do it (e.g., before meals and before bedtime), and how often they will perform the target behavior (e.g., daily). They will also receive a 14-page educational packet, with age-appropriate information from the American Diabetes Association website on the following topics: understanding A1C, driving and diabetes, hyper- and hypoglycemia, and sports and exercise.

Participants randomized to the TXT group will complete a behavioral health contract. They will also receive an educational packet, with age-appropriate information from the American Diabetes Association website (e.g., understanding A1C, driving and diabetes). Adolescents in the TXT group will also complete a positive affect interview at baseline with a trained research assistant. During the positive affect interview, adolescents will be asked to list three things that make them feel good, even for just a few minutes. Next, they will be asked to choose two to three values that they personally found to be most important from the following list: Enjoying Sports, Art, Working Hard in School, Having a Sense of Humor, Being Creative, Belonging to a Social Group or Club, Following Politics or Current Events, Relationships with Friends, Relationships with Family, Faith or Spirituality, Music. The adolescents will write a few short sentences about why those values are important to them, and to provide an example of a time they accomplished something or had a good experience related to that value. Further, parents will be asked to provide positive affirmations (praise or positive messages) to their adolescents, focused on non-diabetes strengths. Parents will be given examples of messages and asked to write a sample positive message. The trained research assistant will give parents feedback on their messages to ensure that they meet the requirements.

A brief assessment of positive affect (Positive and Negative Affect Scale -- Child -- Short Form), consisting of 10 items, will be obtained from all adolescents via automated text messaging twice/month during the 8-week intervention. All adolescents will also be sent a retention item (e.g., laptop decal) halfway through the 8-week intervention period.

Follow-up data (self-report measures and clinical data) will be collected at 3 months, 6 months, and 12 months after enrollment in REDCap. In addition, teens and parents will be invited to participate in an exit interview at the 3-month follow-up data collection.

After completing the exit interview participants who currently use or have used a CGM will be offered the opportunity to participate in a secondary study to understand how adolescents use CGM to manage their diabetes. This will be a 1 time zoom interview that lasts approximately 45 minutes.

#### 6.1.2 Administration and/or Dosing

Adolescents in the TXT group will receive automated text messages 5 days/week for 8 weeks. Messages will be tailored to include adolescents' responses to the baseline interview, including reminders to engage in gratitude and self-affirmation. Gratitude messages (e.g., "Last week you said [response from gratitude exercise] made you happy. Have you noticed that this week, even for a few minutes?") will be sent once/week. Important value messages (e.g., "You mentioned that [response from values exercise] was important to you, and I asked you to think about that when it was hard for you to check your blood sugar. Have you done that this week?") will be sent once/week. Mood Booster messages will be sent 2-3 times/week. Mood Boosters include inspirational messages (e.g., "Believe you can, and you're halfway there!") and humorous messages (e.g., "Which hand is it better to write with? A: Neither, it's best to write with a pen!"), based on earlier work to obtain teens' ratings of messages. Younger teens (age 13-14) will receive some different messages than older teens (age 15-17), based on ratings. Additionally, to induce positive mood, teens will be texted gift cards codes valued at \$5.00 on alternating weeks. Parents will receive weekly text message reminders to provide positive messages to their teens.

### 6.2 FIDELITY

#### 6.2.1 INTERVENTIONIST TRAINING AND TRACKING

Trained Key Study Personnel will administer the health behavior contract and conduct the positive affect interview.

### 6.3 MEASURES TO MINIMIZE BIAS: RANDOMIZATION AND BLINDING

The randomization scheme will be determined by the biostatistician, and adolescents will be stratified by diabetes device use (insulin pumps, continuous glucose monitors).

## 7.1 DISCONTINUATION OF STUDY INTERVENTION/EXPERIMENTAL MANIPULATION

If participants ask to be withdrawn from the study, the reason(s) for discontinuing the participant from the intervention, and methods for determining the need to discontinue will be documented in the study record.

## 7.2 PARTICIPANT DISCONTINUATION/WITHDRAWAL FROM THE STUDY

Participants are free to withdraw from participation in the study at any time upon request.

An investigator may discontinue a participant from the study for the following reasons:

- Significant study intervention non-compliance
- Lost-to-follow up; unable to contact subject
- Any event or medical condition or situation occurs such that continued collection of follow-up study data would not be in the best interest of the participant or might require an additional treatment that would confound the interpretation of the study
- The participant meets an exclusion criterion (either newly developed or not previously recognized) that precludes further study participation

The reason for participant discontinuation or withdrawal from the study will be recorded in the REDCap database. Subjects who sign the informed consent form and are randomized but do not receive the study intervention may be replaced. Subjects who sign the informed consent form, and are randomized and receive the study intervention, and subsequently withdraw, or are discontinued from the study, will not be replaced.

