## 8 STUDY ASSESSMENTS AND PROCEDURES

### 8.1 ENDPOINT AND OTHER NON-SAFETY ASSESSMENTS

Follow-up data will be collected at 3 months, 6 months, and 12 months.

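### Section 7.2 lets an investigator remove a participant from the study for undefined intervention non-compliance, against the Section 5.3 aim of collecting data regardless of engagement

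*Combined protocol and SAP*

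**What the plan says.** Section 7.2 introduces its list with "An investigator may discontinue a participant from the study for the following reasons", and the first reason is "Significant study intervention non-compliance". The removal is from the study, not only from the intervention. No threshold for significant non-compliance appears anywhere.

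Section 5.3 points the other way. Its stated aim is to secure "participation in data collection regardless of their engagement in the text messages so that intent-to-treat analyses may be conducted".

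Section 7.1 is headed as the section on discontinuing the intervention, but its single sentence begins "If participants ask to be withdrawn from the study, the reason(s) for discontinuing the participant from the intervention". It deals with requests to leave the study and the recording of reasons, and does not mention continued follow-up. Section 7.3 covers missed visits and loss to follow-up.

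On timing, Section 8.1 says "Follow-up data will be collected at 3 months, 6 months, and 12 months", and Section 6.1.2 gives 8 weeks of texts. Section 9.3.1 analyses anyone with a baseline outcome and at least one later outcome.

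Section 7.2 also says "Subjects who sign the informed consent form and are randomized but do not receive the study intervention may be replaced", without saying whether the replaced participant is still followed and analysed.

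**The concern.** An adolescent who ignores the texts is the kind of participant Section 5.3 wants to keep in the data and Section 7.2 allows to be removed. Site staff are not told which section prevails.

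The consequence depends on timing. Someone removed after a follow-up A1C stays in the analysis under Section 9.3.1. Someone removed during the 8 intervention weeks has no follow-up outcome yet and would leave it.

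Use of the permission could differ by arm. Non-compliance can be seen in both arms, since everyone has a health behavior contract and receives the affect assessment by text (Section 6.1.1). But the tailored messages 5 days a week and the parental affirmations exist only in the texting arm (TXT), and Section 6.3 describes no blinding despite its heading. If removals are unequal and the removed adolescents have a different A1C course, the arms compared are no longer the arms randomised, and no model can recover outcomes that were never collected.

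**Working it through.** **Reading the sections together.** Because Section 7.2 is permissive, a site can satisfy both 7.2 and 5.3 by never using the non-compliance reason. This is a tension, not a flat contradiction. Once the permission is used, the Section 5.3 aim fails for that participant. Another reason in the same Section 7.2 list concerns cases where continued collection of follow-up data is not in the participant's interest. That supports reading removal from the study as the end of data collection, though this remains an inference.

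**The plan's own figure.** 200 × (1 − 0.15) = 170, as Section 9.2 states, or 85 per arm. The 90% power statement could not be checked, because the effect-size table is not in the text available.

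**Assumed inputs.** The documents give no rate of removal for non-compliance. All of the following except 85 per arm are assumptions.
- A1C SD 1.5 points; correlation between visits r = 0.7.
- d = 0.5 points: how much worse the removed TXT adolescents' A1C change is than that of those retained, after the model covariates.
- q = 2% or 9% of TXT removed before 3 months, none in the education arm (EDU). These are the all-cause losses implied by "excellent retention rates (91-98%) in our pilot studies", so they attribute a great deal to this one rule.
- Removals count inside the planned 15% loss, leaving 85 analysed per arm.
- Two-sided test at 0.05.

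**3-month contrast.**
- Shift = q × d: 0.02 × 0.5 = 0.010 points; 0.09 × 0.5 = 0.045 points, in favour of TXT.
- SE = SD × √(2(1 − r)) × √(2/85) = 1.5 × 0.775 × 0.153 = 0.178.
- Type I error = Φ(−1.96 + shift/SE) + Φ(−1.96 − shift/SE): 5.04% at q = 2%, 5.73% at q = 9%.

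**Treatment-by-time test, 3 df**, with the same shift at 3, 6 and 12 months under compound symmetry.
- V = SD² × (1 − r) × (I + J) × (2/85), where I is the identity matrix and J the matrix of ones. The noncentrality is shift′V⁻¹shift, which reduces to 0.75 × shift² / (SD² × (1 − r) × 2/85).
- q = 2%: noncentrality 0.0047, type I error 5.03%.
- q = 9%: 0.75 × 0.045² / (2.25 × 0.3 × 2/85) = 0.0956, type I error 5.57%.

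**Sensitivity.**

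| Case | 3-month | 3 df |
|---|---|---|
| q = 9%, d = 0.5, SD 2.0, r 0.5 | 5.2% | 5.2% |
| q = 9%, d = 0.5, SD 1.5, r 0.7 | 5.7% | 5.6% |
| q = 9%, d = 0.5, SD 1.2, r 0.85 | 7.3% | 6.8% |
| q = 9%, d = 0.25, SD 1.5, r 0.7 | 5.2% | 5.1% |
| d = 0, or equal removal and gap in both arms | 5.0% | 5.0% |

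A reversed gap reverses the direction. A simulation of 20,000 trials at q = 9%, d = 0.5 agreed with the base case: 5.7% for the 3-month contrast and 5.6% for the 3-df test.

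**Power**, under a different assumption: 10% of TXT removed on top of the 15% dropout, so 75 + 85 = 160 analysed. By a simple two-sample formula, an effect of 0.497 SD that had 90% power with 85 per arm has 88.1%. The power loss is minor; selective removal matters more.

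**The case against.** The strongest reply is that the intention is already clear. Section 5.3 speaks specifically to low text engagement and names intent-to-treat, while Section 7.2 offers only a general discretion. This stands in part: it is why the point is a tension. But Section 5.3 is a retention aim, Section 7.2 is the operative withdrawal rule, and nothing ranks them.

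It is also uncertain that a removed adolescent would have no follow-up A1C. The documents do not say whether routine clinic values would still be used, and the summary of changes shows that the team sought agreement to collect A1C even from people who were screened but not enrolled. That stands as a caution; it does not establish that values would be kept after removal.

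The window is narrow and the magnitude is stacked. The 9% case puts all of the worst pilot loss on one rule, although Section 7.2 lists loss to follow-up separately, and assumes none in EDU. The 7.3% figure arises from holding the gap at 0.5 points while the SD of change falls to 1.2 × √0.30 = 0.66. The gap is then 0.76 SD of change, against 0.5/1.16 = 0.43 in the base case. With the gap scaled to the SD of change, the 3-month figure stays at 5.7% throughout. All of this is correct, and 7.3% should not be read as evidence of harm.

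Finally, Section 9 does not state analysis by assigned arm, but nothing in the plan suggests reassignment. Few participants should qualify for replacement either, since Sections 1.3 and 4.3 place the contract and the positive affect interview at the first visit, as Section 1.3 does randomisation and the educational materials. Both are mainly drafting points, and the conclusion does not rest on them.

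**Conclusion.** The concern holds as a cheap improvement. The plan permits removal from the study on an undefined ground that works against its own intent-to-treat aim, and it has no route for follow-up off the intervention.

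Bias requires all of these: use before the 3-month A1C, unequal use by arm, and a difference in A1C course beyond what baseline A1C, age, sex and race/ethnicity explain. If any fails, there is little or none. Neither size nor direction is fixed by the documents. Under the base assumptions the effect runs from negligible (2% removed) to small (9% removed, 0.045 points). Confidence is medium, because the wording is plain but how it would be applied is unknown.

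**What to change.** Reconcile Sections 5.3, 7.1, 7.2 and 9.3.1 so that intervention non-compliance alone does not end A1C and questionnaire collection, subject to consent and to the existing best-interest provision in Section 7.2. As supporting wording, state in Section 9 that all randomised participants, including any who are replaced, are analysed in their assigned arm using every available A1C. Report discontinuations by arm and reason from the REDCap record that Section 7.2 already requires.

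The cost is protocol and SAP wording, plus a check that the consent form, which is not in this file, covers follow-up after the intervention stops. Routine-visit A1C, the home A1C kit and the survey follow-up process already exist in Section 5.3.

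The change helps only visits still to come. The summary of changes shows that many participants had been enrolled by May 2021, and outcomes already missed cannot be recovered; the analysis statement and the reporting remain useful. The downside is a slightly diluted effect estimate from keeping non-engagers.

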## 4 STUDY DESIGN

### 4.1 OVERALL DESIGN

To test the effects of the proposed intervention, we will recruit a sample of 200 adolescents with T1D and their parents from two clinical sites (Vanderbilt University Medical Center and Children's National Medical Center, 100 dyads from each site). Adolescents will be eligible if they (1) are between the ages of 13-17; (2) have been diagnosed with T1D for at least 12 months; (3) score above the clinical cutoff on a screening tool for diabetes distress; and (4) speak and read English. The sampling goal for this study across the two sites is 68% white, 10% Hispanic, 16% Black, and 6% Asian, with equal numbers of boys and girls, in line with recent studies conducted in these settings.

If the adolescent is eligible, the RA will obtain informed consent/assent, and the adolescent and his/her parent will complete the baseline measures. Participants will then be randomly assigned to one of two conditions: Positive Affect and Education (n=100) or Education only (n=100). Randomization will be stratified by use of diabetes devices (insulin pump and CGM), to avoiding confounding effects. A computer program will generate the randomization scheme.

After completing the exit interview, participants who use/have used a continuous glucose monitor (CGM) will be offered the opportunity to participate in a secondary study to discuss the role of CGM in their diabetes management.

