## 9 STATISTICAL CONSIDERATIONS

### 9.1 STATISTICAL HYPOTHESES

- Primary Efficacy Endpoint(s):

The primary outcome is change in glycemic control (A1C). To test Aim 1, a linear mixed effects regression model will be used to estimate the effect of intervention over time on glycemic control (A1C).

- Secondary Efficacy Endpoint(s):

Our secondary outcomes are diabetes distress, coping, and diabetes management. To test Aim 2, separate linear mixed effects regression models will be used to estimate the effect of the intervention over time on diabetes distress (PAID-T), coping (RSQ), and diabetes management (P-SCI, SCI, Checks/Day). Qualitative methods will be used to code data from the secondary CGM interview study into appropriate themes that then guide analysis.

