### 9.3 STATISTICAL ANALYSES

#### 9.3.1 General Approach

Outcomes will be measured at up to four time-points per subject (baseline, 3 months, 6 months, and 12 months), so we will use time, treatment group and the interaction of treatment with time serving as the main explanatory variables. Such a model will allow us to test for any differences between treatment and control groups at 3, 6 or 12 months while accounting for baseline values. While the randomized block design should minimize confounding, we will adjust for age, sex, and race/ethnicity to improve precision. The results from the adjusted and unadjusted models will be compared with respect to their estimates of the treatment effects. We will include a random intercept to account for within-subject correlation arising from taking repeated measurements on the same subject over time. The error structure of the model is assumed to be compound symmetric, and the validity of this assumption will be examined by computing Akaike Information Criteria against other common structures. Subjects will

be included in the analysis if they have an outcome measured at baseline and at least one outcome measured at 3, 6 or 12 months.

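### Section 7.2 permits ending a randomised teen's follow-up because an event might call for extra, confounding treatment, which works against the intent-to-treat aim

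*Combined protocol and SAP*

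**What the plan says.** Section 7.2 introduces its list with "An investigator may discontinue a participant from the study for the following reasons". The third reason joins two grounds. One is that further data collection would not be in the participant's best interest. The other is that an event, condition or situation "might require an additional treatment that would confound the interpretation of the study". The removal is from the study, not only from the text messages.

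Section 7.1 asks only that reasons and methods be documented. Neither it nor sections 7.2 to 8.1 say that A1C is still collected after an investigator-led discontinuation.

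Section 5.3 commits the team to keeping families in "participation in data collection regardless of their engagement in the text messages so that intent-to-treat analyses may be conducted". Section 9.3.1 limits the analysis to participants with a baseline value and "at least one outcome measured at 3, 6 or 12 months". On the model it says: "We will include a random intercept to account for within-subject correlation". No sensitivity analysis for informative missing data is described. Section 6.3, on minimising bias, covers the randomisation scheme and stratification by device use. It does not describe blinding of whoever decides on removal.

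**The concern.** The best-interest ground protects the participant. The confounding ground protects the interpretation of the study, and it does so in the wrong direction. In an intent-to-treat comparison, treatment added after randomisation is part of what follows from assignment. Ending measurement because of it makes the set of observed outcomes depend on a post-randomisation event.

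The threshold is also low. The wording covers treatment that might be needed, so removal can come before any such treatment starts. If removal rates differ between arms, or if the teens removed differ in outcome between arms, the A1C comparison is biased. The mixed model does not repair this when the reason for removal carries information about unobserved later values.

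**Working it through.** **1. What is lost, by timing of removal** (section 7.2 read with section 9.3.1)

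- Before any follow-up value: the teen is not in the analysis set.
- After the 3-month visit: the 3-month value stays, and the 6- and 12-month values are lost. The synopsis names 3 months as the primary endpoint, so that value is unaffected.

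**2. The plan's own figure.** Section 9.2: 200 × (1 − 0.15) = 170 analysed. This reproduces. The detectable effects in Table 3 are not in the available text, so I use a simple yardstick: two arms of 85, two-sided 0.05 (section 9.2 does not state sidedness), 90% power, no baseline adjustment. Detectable difference = (1.960 + 1.282) × √(2/85) = 0.497 SD.

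**3. Upper bound on the bias, with assumed rates.** Suppose that removal takes exactly the worst A1C changes, all before 3 months, and that changes are normal with equal SD in both arms. Removing the upper fraction p shifts the arm mean by φ(z)/(1 − p), where z is the 1 − p quantile.

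| Share removed, p | Shift in arm mean (SD) |
|---|---|
| 10% | 0.195 |
| 5% | 0.109 |
| 8% | 0.162 |
| 2% | 0.049 |

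- 10% of education v 5% of texting: 0.195 − 0.109 = 0.086 SD; 0.086/0.497 = 17% of the yardstick.
- 8% v 2%: 0.162 − 0.049 = 0.112 SD after rounding; 0.112/0.497 = 23%.
- Equal shares: near zero.

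**4. Imperfect selection.** If the trigger and A1C change are jointly normal with correlation ρ, the bias is multiplied by ρ. For 10% v 5%:

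- ρ = 0.3: 0.3 × 0.086 = 0.026 SD (about 5% of 0.497).
- ρ = 0.5: 0.5 × 0.086 = 0.043 SD (about 9%).

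**5. Second method, in A1C points.** If removed teens run D points above retained teens, and shares pT (texting) and pC (education) are removed before 3 months, the bias in texting minus education is (pC − pT) × D. D is assumed to be 0.5 to 2.0.

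| Texting v education removed | Bias (A1C points) |
|---|---|
| 2% v 5% | 0.015 to 0.06 |
| 2% v 10% | 0.04 to 0.16 |
| 10% v 5% | −0.025 to −0.10 |
| equal | 0 |

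A small simulation of the random-intercept model (60 runs, 100 per arm, assumed shift of 1.5 points, 3% v 10% removed before 3 months) gave a bias of about 0.10 points at 3 and 12 months. The formula gives 0.07 × 1.5 = 0.105. With 7% removed in each arm the bias was about zero.

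**6. Precision.** At an effect that gives 90% power with 85 per arm, 80 per arm gives 88.2% and 75 per arm gives 86.1%. The issue is bias, not sample size.

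**The case against.** The strongest case against the point is that the clause is permissive, reasons are recorded in REDCap, and no removal rate is given. The assumed rates are also high by the plan's own standards. 10% v 5% averages 7.5%, half of the 15% attrition planned for all causes, and the pilot retention of 91–98% in section 5.3 implies a 2–9% loss from all causes. All of this stands. It is why the figures above are upper bounds and not estimates.

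A reader might also infer more than the documents support:

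- *That the rule deletes the worst-doing teens.* It removes a teen from the analysis only if no follow-up value exists yet. The trigger is any event, condition or situation. A link to rising A1C or distress is plausible but not stated.
- *That investigators who know the arm make the decision.* Section 6.3 is silent. The most that can be said is that arm-dependent removal is not ruled out.
- *That the bias runs toward no effect.* That needs more removals, or worse outcomes among those removed, in the education arm. The opposite pattern reverses the sign.
- *That section 7.2 flatly contradicts section 5.3.* The section 5.3 sentence speaks of engagement with the text messages. Its direct collision is with the non-compliance reason in section 7.2. For this clause the conflict is with the intent-to-treat principle that the sentence invokes.

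It is also fair to object that striking this clause alone is not enough. Another intervention or a serious interfering condition is an exclusion criterion in section 5.2, and a newly developed exclusion criterion is itself a reason for removal in section 7.2. The fix therefore has to reach beyond this one clause.

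**Conclusion.** The point holds as a defect in the rule, not as a demonstrated bias. Section 7.2 permits ending follow-up on a ground that intent-to-treat does not accept. Nothing in the plan keeps A1C collection going afterwards, and section 9.3.1 has no analysis that would recover what is lost.

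The size and direction of any bias are unknown. The values of 0.086 and 0.112 SD are ceilings for the assumed rates. They rest on perfect selection of the worst changes, removal before 3 months, and unequal removal between arms. Weaker selection shrinks them in proportion (0.026 SD for 10% v 5% at a correlation of 0.3), and equal removal brings them close to zero. This is a cheap improvement that is worth making. It does not invalidate the trial.

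**What to change.** In section 7.2:

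1. Delete the words "might require an additional treatment that would confound the interpretation of the study" and the conjunction that joins them to the best-interest ground. Leave the best-interest ground as it is.
2. State that any extra treatment is recorded with its date. Scheduled A1C and questionnaire collection then continues unless consent or assent is withdrawn or collection is against the participant's interest. All values are analysed in the assigned arm.
3. State that stopping the intervention is separate from stopping follow-up, so that the other listed reasons do not bring the same removal back. This also brings sections 5.3, 7.2 and 9.3.1 into line.

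The cost is a few sentences in section 7.2 and one dated field in REDCap. No care decision changes. The downside is that the estimate then includes the effect of any extra treatment, which is what intent-to-treat requires.
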